### **III. STUDY METHODOLOGY:**

#### Study design:

Single center, prospective, randomized, placebo controlled double-blind trial.

#### Inclusion criteria:

1. Necrotizing soft tissue infection by clinical diagnosis and requiring surgical treatment.
2. Sepsis by clinical diagnosis and/or by Sepsis-3 criteria, with source attributed to the wound.
3. Anticipated or confirmed intensive care unit admission.

#### Exclusion criteria:

Adapted from VICTAS protocol:

1. Age < 18 years of age
2. Weight < 40 kg
3. Prior enrollment in this study or current enrollment in another study of any kind
4. Surgical findings, pathology/histology findings, or other findings determined to be inconsistent with an infectious acute NSTI such that the clinical diagnosis is no longer that of a NSTI
5. Sepsis deemed unlikely
6. Limitations of care during enrollment [defined as refusal of cardiovascular and respiratory support modes described in inclusion criteria, including “do not intubate” (DNI) status and comfort care]
7. Known allergy or known contraindication to vitamin C, thiamine, or corticosteroids (including previous history or active diagnosis of primary hyperoxaluria and/or oxalate nephropathy, or known/suspected ethylene glycol ingestion, or known G6PD Deficiency)
8. Use of vitamin C at a dose of >1g/day (IV or oral) within the 24 hours preceding first episode of qualifying organ dysfunction during a given ED or ICU admission
9. Chronic disease/illness that, in the opinion of the site investigator, have an expected lifespan of < 30 days unrelated to current sepsis diagnosis (e.g., stage IV malignancy, neurodegenerative disease, etc.)

10. Kidney Stone(s) of any kind
11. History of Oxalate Kidney Stone(s)
12. Pregnancy or known active breastfeeding
13. Prisoner or Incarceration
14. Inability or unwillingness of subject or legal surrogate/representative to give written informed consent

Comparator:

Patients randomized to not receive HAT will comprise the control group and those randomized to receive HAT will comprise the treatment group.

Surgeons and surgical performance:

This study will not affect the surgical care of the patient. Patients with known/suspected NSTI will undergo surgery urgently/emergently as before. Patients who consent for and meet criteria for this study will be randomized, to either receive or not receive HAT. Care is otherwise identical for patients in each group. The only difference in the care of these patients will be in whether or not they receive HAT. The only surgeons who will be involved are those on the Burn service.

Study Site:

Ascension Via Christi Hospital – St. Francis Campus, Wichita, Kansas.

Duration of Treatment:

Patients will be enrolled within 24 hours of diagnosis of sepsis related to a NSTI. HAT will be initiated within 4 hours of enrollment (thus treatment with HAT can occur no later than 28 hours from diagnosis).

Per [name] original study, HAT consists of:

- 1) 1.5 g vitamin C every 6 hours for 4 days or until ICU discharge
- 2) 50 mg hydrocortisone every 6 hours for 7 days or until ICU discharge (followed by a taper over 3 days)
- 3) 200 mg thiamine every 12 hours for 4 days or until ICU discharge

In our study, due to the prolonged ICU course typical of most patients with NSTIs, it is not felt feasible to continue indefinitely "until ICU discharge." Thus, treatment will be continued for 4 to 7 days plus a 3 day taper (respectively) as above, with no plan for a longer duration of treatment.

The control arm will receive the same standard ICU care for NSTI but will not receive HAT. They will receive a placebo consisting of normal saline, indistinguishable to the treatment team (blinded) but known to the pharmacy team (unblinded to treatment and placebo groups). This is so that if the treatment team elects to give stress dose steroids, they can be administered without breaking protocol (i.e. if the patient is getting HAT, it includes steroids, so if the treating team wanted to start hydrocortisone - because they didn't know if the patient was on HAT or placebo and felt steroids were indicated - the pharmacist could ensure the patient was on steroids one way or another without unblinding the providers).

Duration of Study:

The study enrollment period will continue for one year after its initiation, or until enrollment goal is met. Patients will be followed until hospital discharge.

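### Exclusion 8 ties the vitamin C look-back to a qualifying organ dysfunction that this protocol does not define, so some patients given high-dose vitamin C before randomisation are eligible as written

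*Combined protocol and SAP*

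**What the plan says.** The exclusion list in section III is headed "Adapted from VICTAS", so it was taken from another trial's protocol and modified.

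- **Exclusion 8** concerns vitamin C above 1 g/day, IV or oral. Use counts only if it falls "within the 24 hours preceding first episode of qualifying organ dysfunction during a given ED or ICU admission".
- **Exclusion 6** concerns limitations of care, "defined as refusal of cardiovascular and respiratory support modes described in inclusion criteria", and then gives do-not-intubate status and comfort care as included cases.
- **Inclusion criteria** are three: an NSTI needing surgery; "Sepsis by clinical diagnosis and/or by Sepsis-3 criteria"; and ICU admission, anticipated or confirmed. None names an organ dysfunction as qualifying, and none describes a support mode. Neither is defined elsewhere in the document.
- **Timing** (Duration of Treatment): "Patients will be enrolled within 24 hours of diagnosis of sepsis related to a NSTI". HAT starts within 4 hours of enrolment, so no later than 28 hours after diagnosis. Randomisation follows consent (Patient Enrollment and Random Assignment).
- **Data**: the variable list in section III has a field for active systemic steroid use at baseline but none for prior vitamin C. The Data Collection paragraph also points to an attached spreadsheet, which is not shown.

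**The concern.** An eligibility rule has to be applicable to every screened patient when eligibility is decided. Exclusion 8 depends on an event that some eligible patients will not have had. In others the event happens hours before randomisation, and the rule says nothing about the time in between.

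Vitamin C is one of the three components under test, and the exclusion evidently exists to keep recent high-dose users out. The hours just before randomisation hold the exposure closest to study treatment, and those are the hours the rule can miss. A patient who has already had high-dose vitamin C and is then allocated to placebo is a partly treated control. Because the exposure precedes randomisation, it is balanced between the arms in expectation. The consequence is dilution of the treatment contrast, not confounding.

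**Working it through.** **Timing figure.** 24 h to enrolment + 4 h to first dose = 28 h, which matches the plan.

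**Timeline.** Put sepsis diagnosis at time 0 and organ dysfunction onset at −d hours (d ≥ 0). Put randomisation at r hours, with r ≤ 24, taking it to occur at enrolment.

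- Look-back as written: from −d−24 to −d.
- Uncovered interval before randomisation: from −d to r, length d + r.
- With d = 0 and r = 24: 0 + 24 = 24 h uncovered before randomisation, and up to 28 h before first dose. If onset precedes diagnosis, d adds to both.

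**Three patients under exclusion 8 as written** (illustrative times; vitamin C above 1 g/day in each case):

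| Patient | Vitamin C use | Result |
|---|---|---|
| Onset at 0, randomised at 24 h | 12 h before onset | Excluded |
| Onset at 0, randomised at 24 h | Started 6 h after onset | Not excluded |
| Clinical sepsis, no organ dysfunction by randomisation | Any time | No anchor; rule cannot be applied |

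The rule works in the first row and fails in the other two.

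**Does another provision close the gap?** No other exclusion mentions prior vitamin C intake; exclusion 7 covers only allergy and contraindication. The document has no concomitant-medication rule for vitamin C. The pharmacy arrangement under Duration of Treatment deals with open-label steroids only.

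**Which window would close it?**

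- *24 h before randomisation only.* Take the first-row patient: use at −12 h, randomisation at 24 h. The use is 24 + 12 = 36 h old at randomisation. This patient is excluded now and would become eligible, so the simple re-anchoring opens a new gap.
- *From 24 h before sepsis diagnosis to randomisation.* This runs from −24 to r, at most 24 + 24 = 48 h. All three rows can be decided, and the uncovered interval before randomisation is 0 h.
- *Residual case.* If onset precedes diagnosis by 6 h and use was 28 h before diagnosis, that use is 28 − 6 = 22 h before onset. It is excluded now but lies outside the window starting at −24 h. Starting from the earlier of diagnosis and documented onset would keep such a patient out.

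**Sample size, for context.** Inputs from section VII: 20% versus 4.24% mortality, α = 0.05, power 80%; two-sided per section VI. With p̄ = (0.20 + 0.0424)/2 = 0.1212:

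n = [1.960·√(2·0.1212·0.8788) + 0.842·√(0.20·0.80 + 0.0424·0.9576)]² / (0.20 − 0.0424)² = (0.9046 + 0.3770)² / 0.1576² = 66.1

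That rounds up to 67 per group, against 66 in the plan, and power at 66 is 79.9%. The plan's figure is reproduced to within rounding. Nothing in this point changes it.

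**The case against.** **The rule still does work.** Exclusion 8 removes anyone with high-dose use in the 24 hours before an identifiable onset. For patients entering by Sepsis-3, a reader could take the onset of organ dysfunction from the cited definition. Both points stand, so the gap concerns some high-dose users, not all. But the protocol does not make the Sepsis-3 link, the link would not help patients entering by clinical diagnosis alone, and the window would still close at onset.

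**Nothing shows that such use occurs.** The plan says care is otherwise identical in the two arms and that controls get standard ICU care without HAT. No document reports open-label high-dose vitamin C at this site. This stands, and it is why the effect cannot be sized.

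**A reader might infer a material loss of power.** Suppose a share f of controls were pre-exposed and gained a fraction g of the planned benefit. The control rate would be 20 − f·g·15.76 points. With 66 per arm and f assumed at 5%, 10% or 20%:

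- g = 1: power 76.8%, 73.4% or 65.8%, against 79.9%.
- g = 0.25: power 79.2%, 78.4% or 76.8%.

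The documents supply neither f nor g. Setting g = 1 credits vitamin C alone with the whole three-drug effect, and g = 0.25 assumes benefit proportional to dose (24 h at the regimen's 6 g/day is 4 of 16 doses). These figures show the direction only and do not measure the problem.

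**A reader might infer that exclusion 6 lets in patients who decline vasopressors**, putting misleading zeros into vasopressor duration. The text does not support this. It excludes "refusal of cardiovascular and respiratory support modes described in inclusion criteria" and gives its two examples as included cases, not as a full list. Even with the cross-reference empty, refusal of cardiovascular support is excluded on a plain reading.

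**A reader might infer that the exposure could never be detected.** That is not supported either. The attached spreadsheet may hold such a field, and most data come from the electronic chart, so in-hospital doses are likely to be retrievable.

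**Conclusion.** The point holds for exclusion 8. Its anchor is undefined in this trial, and the rule as written admits some patients it was meant to keep out: those with clinical sepsis and no organ dysfunction, and those first given high-dose vitamin C between onset and randomisation. This follows from the text and needs no assumption beyond taking randomisation to occur at enrolment. The uncovered interval is up to 24 hours if onset coincides with diagnosis, and longer if onset is earlier.

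The consequence is dilution of the HAT versus placebo contrast. Its size is unknown because the frequency of such use is not given, and it is probably small. Sample size and significance level are unaffected. The change is worth making because it is cheap and protects the treatment contrast, not because a bias has been demonstrated.

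The empty cross-reference in exclusion 6 is a secondary wording point with no demonstrated effect on any outcome.

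**What to change.** 1. **Exclusion 8.** Reconcile it with the inclusion criteria and the enrolment window. Anchor the look-back to events that every patient has and run it through randomisation, for example from 24 hours before the sepsis diagnosis up to randomisation, keeping the protocol's own threshold of more than 1 g/day. If the investigators also want to keep out everyone excluded now, the start can be the earlier of sepsis diagnosis and documented onset of organ dysfunction. A window of only 24 hours before randomisation should not be used, for the reason shown in the working.
2. **Data.** Add one yes/no field for vitamin C use above the threshold in that window, unless the attached spreadsheet already has one.
3. **Exclusion 6.** Reconcile the reference to support modes with the inclusion criteria, which describe none. Which modes to name is for the investigators.

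The cost is a short amendment to two criteria and at most one field, which can be filled from the medication record and history. The downside is that a few patients given high-dose vitamin C before randomisation become ineligible, in a trial that needs 132 participants at a single centre.

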**Data Collection:**

Data will be recorded prospectively by IRB approved study personnel and entered into a shared spreadsheet on the Ascension Google Drive. See the attached spreadsheet for the specific data to be collected.

**Variables collected will include:**

- Patient name
- Medical record number (FIN)
- Date of birth
- Date and time of diagnosis of NSTI
- Date and time of randomization
- Time from diagnosis of NSTI and sepsis to initiation of HAT: hours.
- Time on pressors prior to initiation of HAT: hours
- Patient demographics (age, gender)
- Location of NSTI infection
  - Perineum
  - Genitalia
  - Groin
  - Lower extremity
  - Upper extremity
  - Hand
  - Foot
  - Head/Neck
  - Back
  - Chest
  - Abdomen
  - Multiple/Other – free text
- Preexisting conditions – similar to [name] study:
  - None
  - Diabetes mellitus
  - Hypertension
  - Heart failure
  - Malignancy
  - Chronic obstructive pulmonary disease
  - Cirrhosis
  - Cerebrovascular accident
  - Acute Kidney Injury (AKI)
  - Chronic kidney disease
  - Morbid obesity (weight and height)
  - Immunocompromised (HIV infection, neutropenia, post-transplantation, other)
  - Active medical systemic steroid use at baseline
  - Illicit drug use evident by patient history or drug screen
  - Active tobacco or nicotine product use
- Time from diagnosis of NSTI to surgery: hours

- Total number of visits to the operating room for NSTI-related surgical intervention
- Identification of NSTI derived from pressure-related injury
- Wound status at time of ICU discharge:
  - Open
  - Closed
- Duration of vasopressor therapy: hours cumulative from entire hospitalization
- Positive blood cultures (Y/N)
- Organism present on wound culture
- Time to antibiotic use
- Antibiotic used
- Requirement for renal replacement therapy in patients with AKI (Y/N)
- Procalcitonin level daily for 4 days (with day one being admission/enrollment, then 3 days after, totaling 4 days of treatment with HAT)
- Daily SOFA score for 4 days (with day one being admission/enrollment, then 3 days after, totaling 4 days of treatment with HAT)
- Total ventilator days
- ICU LOS: Days
- Hospital length of stay: Days
- Discharge disposition: alive or deceased
- If the patient withdrew: Y/N
- Reason for patient withdrawal: Free text

Population:

All adult patients presenting to Ascension Via Christi Hospital St Francis will be screened for inclusion and exclusion criteria. Once a potential study participant has been identified, a member of the study team will approach the patient or the patient's legal representative regarding inclusion into this study, and consent will be obtained. The length of the enrollment period of this study will be one year from the start of the study, or until the enrollment goal is met. Participants will be followed until hospital discharge.

Patient Enrollment and Random Assignment:

Patients who are admitted or diagnosed with sepsis secondary to an acute necrotizing soft tissue infection will be provided with the "Patient Informed Consent/HIPAA Authorization" document and will have the study explained to them during their initial evaluation by a member of the study team prior to enrollment. All qualifying patients who choose to participate in the study will sign the consent form, or have it signed by their legal representative. One copy of the consent form will be stored in the patient's chart and a second copy with the Research Scientist in the study files. A third copy of the consent will be provided to the patient for their reference. Randomization will be done via block randomization by the pharmacy department after a patient has consented to participate in the study.

The patient and/or his legal representative will have ample opportunity to decide whether they want to be included in this study and ask questions. The patient will be approached by a member of the study team prior to enrollment. This encounter will be within 24 hours of diagnosis, to provide ample time for consideration and to ask questions. Once consent is obtained, the HAT therapy should be started within 4 hours, such that the maximum possible time to initiation from diagnosis is 28 hours. If the patient meets inclusion criteria, then HAT or placebo (saline) will

be initiated per the randomization protocol, and only the pharmacy team will be unblinded. If the patient's legal representative signs the consent form on behalf of the patient, once the patient regains the ability to make medical decisions for themselves, they will be provided with the consent form and given the opportunity to continue in the study, signing a new consent themselves, or be given the option of discontinuing participation in the study. If the patient chooses to discontinue participation, all study data collected up to that point will be used in the study, although no new patient data will be collected, with the exception of any data needed to monitor the safety of the patient or adverse events in relation to the study treatments already administered.

Potential Risks to Subjects in the Study:

There exists the potential risk of a breach of subject confidentiality during the conduct of this research study. The following will be carried out to maintain patient confidentiality:

All medical information will be protected, and access will be limited to study investigators. Most of the data will be supplied from the electronic charting system at Ascension Via Christi Hospital – St. Francis Campus with patient identifiers (name, date of birth, medical record number [FIN]). The investigators will store data on an Ascension Google Drive. The research team is located in Room 3082 at Ascension Via Christi Hospitals on Saint Francis. The transfer will all occur within [contact] email system, with no one able to view the Google Drive without an Ascension email. No information will transfer outside this system.

Patient identifiers will be kept with the participants PHI while the participant is hospitalized, and study data are actively being collected. Once the participant has been discharged, and all study data has been collected, subject identifiers (subject name, medical record number (FIN), date of birth, date of randomization, and date of procedures) will be maintained on a master list that links the subject to the specific study number. That list will be maintained under secure conditions at all times. Once all data has been deemed complete and analyzed and the work has been accepted for publication, the master list will be destroyed. This will effectively render the list de-identified as no other identifiers will be entered into the data set for analysis. The method in which this will be accomplished is that the master list will be shredded, and any computer file of the master list will be deleted from electronic media. The investigators and designated members of the research team will have access to the study data and will be responsible for data management.

Like any treatment there are potential risks with the administration of HAT, but these are overall low, as evidenced by numerous studies. The most recent large randomized control trial, VICTAS, which examined 501 patients, had no reported serious adverse events and only two adverse events (hemorrhagic shock and decreasing kidney function in the intervention group assessed as potentially related to study participation). In the 2017 Colliou et. al study, vitamin C-related oxalate nephropathy was seen in patients who received higher doses or received doses for a longer duration (1 month – 3 years) than [name] HAT dose. One trial found that hypernatremia was more common in the control group, which the study authors speculated might be due to increased sodium retention from glucocorticoids. GI bleed was another cited complication in this study with an incidence of 3:2 for treatment versus control groups. Like vitamin C, thiamine is a commonly used vitamin and can rarely cause electrolyte abnormalities. Administration of hydrocortisone, a low strength mineralocorticoid, is a commonly used medication in the ICU setting and can rarely cause hypertension or arrhythmia. The risk to

omitting HAT has not been formally studied in this population. Finally, the treatment duration in our study will be limited (i.e. a maximum of 4 days for vitamin C and thiamine and 7 days plus a 3 day taper for hydrocortisone).

The potential risks due to septic shock from a NSTI itself are expected to be no different for patients whether they are enrolled in this study or not.

Evaluations During Treatment:

The evaluation period will begin at the time HAT or placebo is initiated after sepsis criteria is met and end at hospital discharge.

The investigators will collect data as outlined above under “Data Collection.”

Subject Non-evaluability:

Subjects will be deemed non-evaluable and will be dropped from the study if they meet the exclusion criteria and/or elect to withdraw from the study.

Costs

Participants will never be charged for study-related drugs in this study, regardless of the group to which they are randomized. This means that participation in this study will not cost participants more or less than the cost of normal care. No charges for care other than those that would be normally received will be incurred during the study and the cost for participants' normal care will be the participants' and/or the participants' insurance provider's responsibility.

Participants will not be charged for the drugs used in this study. The pharmacy will be absorbing the costs of the drugs regardless of whether it's thiamine, vitamin C, hydrocortisone, or placebo.

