### **II. STUDY OBJECTIVE:**

Evaluate the impact of HAT therapy versus placebo in the treatment of patients with an acute NSTI and sepsis.

Primary outcome:

1. Hospital survival (including those who die within 24 hours of hospital admission)

Secondary outcomes:

1. Duration of vasopressor therapy
2. Requirement for renal replacement therapy in patients with Acute Kidney Injury (AKI)
3. ICU length of stay (LOS)
4. Change in serum procalcitonin (PCT) over first 72 hours
5. Change in SOFA score over first 72 hours (measured as SOFA score daily for four days, with day one being admission, then 3 days after, totaling 4 days of treatment with HAT)
6. Procalcitonin clearance (formula = initial PCT – 72 hour PCT divided by initial PCT x 100)
7. Number of wound related surgeries
8. Wound status at time of hospital discharge:
  - a. Open
  - b. Closed

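### Vasopressor duration is counted over the whole hospital stay, including hours before randomisation; a lesser point is that SOFA and procalcitonin lack one clear day one (minor)

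*Combined protocol and SAP*

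**What the plan says.** Section II (Study Objective) names duration of vasopressor therapy as secondary outcome 1 and gives no start point. The list of variables in section III supplies one: "Duration of vasopressor therapy: hours cumulative from entire hospitalization". The same list has a separate field, "Time on pressors prior to initiation of HAT: hours". Section VI (Statistical Analysis) sets no time zero or baseline and does not mention that field. Under Evaluations During Treatment, section III starts the evaluation period when HAT or placebo is started.

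For SOFA, section II fixes the four daily scores "with day one being admission, then 3 days after, totaling 4 days of treatment with HAT", while the list of variables has them "with day one being admission/enrollment, then 3 days after, totaling 4 days of treatment with HAT".

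For procalcitonin (PCT), section II gives "Change in serum procalcitonin (PCT) over first 72 hours" without saying when the 72 hours begin. The clearance formula opens "Procalcitonin clearance (formula = initial PCT" and does not say when that value is taken. The list of variables uses the same two-way admission/enrolment wording for PCT as for SOFA.

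Duration of Treatment (section III) allows 24 hours from diagnosis to enrolment and a further 4 hours to the start of HAT. Randomisation follows consent, and its date and time are recorded. Data Collection refers to an attached spreadsheet that is not among the supplied pages.

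**The concern.** An outcome meant to show a treatment effect should start when treatment could first have one. Patients with sepsis may already be on vasopressors while they are diagnosed, consented and randomised. Those hours enter the outcome as written. The separate field shows that the sponsor recognised earlier vasopressor time, but it has no stated use. It also names HAT only, so its meaning in a placebo patient, or in a patient never dosed, is unstated.

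For SOFA and PCT the question is which day is day one. Bare admission is itself unclear. The primary outcome specifies the hospital ("including those who die within 24 hours of hospital admission"), while the inclusion criteria accept "Anticipated or confirmed intensive care unit admission", so ICU admission may still lie ahead at enrolment. Staff could apply different rules to different patients, and an admission origin would use up part of the 72-hour window before any study drug is given.

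The four outcomes touched are vasopressor duration, SOFA change, PCT change and PCT clearance.

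**Working it through.** **1. The plan's own figure.** The only calculated figure is the sample size in section VII: mortality 20% versus 4.24%, alpha 0.05, 80% power, and two-sided by section VI. The pooled formula without continuity correction gives 67 per group against the stated 66, and 66 per group gives 79.9% power. The figure reproduces. It rests on mortality alone, so nothing below changes it.

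**2. Start points side by side.**

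| Outcome | Section II | List of variables, section III |
|---|---|---|
| Vasopressor duration | none | whole hospital stay |
| SOFA change | admission | admission/enrolment |
| PCT change and clearance | none | admission/enrolment |

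Evaluations During Treatment adds a further start point, the start of HAT or placebo. It conflicts with the whole-stay count but does not say that it overrides it.

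**3. Bias in vasopressor hours.** Write each patient's total as pre + post, split at randomisation. The difference in mean totals is (mean pre, HAT − mean pre, placebo) + (mean post, HAT − mean post, placebo). Randomisation makes the first bracket zero in expectation, so the mean difference is not biased.

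**4. Dilution.** Let the control means be m before and M after randomisation. A relative reduction r in post hours becomes r × M/(M + m) in total hours, which is smaller whenever m > 0. This matters directly if the data are log-transformed, since section VI permits transformation where variances are unequal.

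**5. Noise.** Var(total) = SD_pre² + SD_post² + 2ρ·SD_pre·SD_post. The documents give none of these terms, so what follows only illustrates assumed values. Take pre hours as uniform over 0–24 or 0–28 h, so SD = 24/√12 = 6.9 h or 28/√12 = 8.1 h, with ρ from 0 to 0.3. Take 66 per group and an effect with 80% power on post hours, δ = SD_post × (1.96 + 0.84) × √(2/66).

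| Assumed SD_post | δ | Power using whole-stay hours |
|---|---|---|
| 24 h | 11.7 h | 69–77% |
| 48 h | 23.4 h | 75–79% |
| 72 h | 35.1 h | 77–80% |

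The direction is also conditional. Whole-stay hours are less variable than post hours when ρ < −SD_pre/(2·SD_post). With SD_pre = 8.08 h this threshold is −0.08, −0.17 or −0.34 for SD_post of 48, 24 or 12 h.

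**6. SOFA and PCT window.** If the first dose is t hours after day one, the share of the window that follows it is (72 − t)/72.

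- Day one at enrolment: t is at most 4, so at least 68/72 = 94%.
- Day one at admission, assuming admission coincides with diagnosis: t is at most 24 + 4 = 28. The share is 94%, 83%, 72% or 61% at t = 4, 12, 20 or 28. At t = 28, 28 h (39%) come before the first dose and 44 h after.
- With daily values assumed at 0, 24, 48 and 72 h, two of four precede the dose at t = 28. Under the enrolment reading only the first can.
- If admission came before diagnosis, the share on the admission reading could be lower still.

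**The case against.** The best reply on vasopressors is that the plan already holds the pieces. The evaluation period starts at HAT or placebo, and total hours minus the pre-HAT field gives hours within it. That is a sensible reading, but the plan never states the subtraction, and the written definition says the opposite. The attached spreadsheet might define the field differently, so the statement that there is only one definition holds for the supplied pages alone.

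On SOFA and PCT the reply is stronger, and most of it stands. Both sections describe the four days as days of HAT treatment, which points to enrolment as day one. On that reading, anchoring at randomisation leaves essentially the same window of at least 68 of 72 hours, so the gain is clarity. The direct conflict concerns SOFA only. PCT is under-specified, because section II gives it no day one that could contradict the list of variables.

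A reader might infer that 39% of the SOFA and PCT window is lost. That needs the literal admission reading, admission coinciding with diagnosis, and the maximum delay at both steps. It describes one extreme patient and not the trial.

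**Conclusion.** The point holds for vasopressor duration: as written, this secondary outcome includes hours that treatment cannot affect, and no section removes or adjusts for them. The consequence is a diluted relative effect and probably more noise. The power figures above rest wholly on assumed standard deviations and correlations, and a sufficiently negative correlation would reverse the effect on noise.

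A reader might infer that the comparison between arms is biased, or that the main result is at risk. The documents support neither. Pre-randomisation hours balance in expectation, and hospital survival and N = 132 do not depend on these definitions.

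The SOFA and PCT part is a wording matter on the likelier reading and costs more only on the literal admission reading. Overall severity is minor.

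**What to change.** Make these changes before any unblinded analysis:

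- **Vasopressor duration.** Define it in sections II and III as cumulative hours after randomisation in both arms, that is, total hours minus hours before randomisation.
- **Pre-treatment field.** Reword it to hours on vasopressors before randomisation, recorded in both arms. The present field runs to the first HAT dose, so it does not give this exactly and has no end point for a patient never dosed.
- **SOFA and PCT.** Delete admission as day one. Take baseline, including the initial PCT, as the last value at or before randomisation, whatever the calendar day. If there is none, use the first value within 4 hours after randomisation and before any study dose. Count the 72 hours from randomisation.
- **Consistency.** Reconcile the evaluation period under Evaluations During Treatment in the same edit, and match the attached spreadsheet if it defines these fields.

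The cost is wording plus one reworded field. That field should be obtainable from the chart, since section III says most data come from the electronic charting system. If SOFA scores and PCT draws are now timed from admission, they move to enrolment and their number is unchanged. The downside is that up to 4 hours between enrolment and first dose are counted, at most 4/72 = 6% of the SOFA and PCT window. These changes do not settle how to handle a patient with no qualifying baseline, or one who dies or is discharged before 72 hours. Both still need a rule.
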